6.7.1. Premedication for Infusions or Injections

Premedication for the study drug infusions or injections is not planned. Any premedication for infusions or injections should be discussed with the medical monitor. Any premedication given will be documented as a concomitant therapy (Section 6.5). Systemic corticosteroids may be permitted if deemed necessary by the investigator.

6.8. Intervention after the End of the Study

6.8.1. Treatment after Study Completion

Mirikizumab will be made available by sponsor to eligible study participants, who complete Visit 19 CCI through the optional Continued Access Period until local commercial availability of mirikizumab and reimbursement, including patient access programs, when and where available. Refer to Section 10.13 for more information on continued access.

7. Discontinuation of Study Intervention and Participant Discontinuation/Withdrawal

These sections describe reasons for:

- permanent or temporary discontinuation of study drug, or
- participant's discontinuation (withdrawal) from the study.

Discontinuation of the study as a whole or of particular study sites is described in Section 10.1.9.

7.1. Discontinuation of Study Intervention

Study drug may be permanently discontinued or temporarily withheld during the study.

Participants who permanently discontinue study drug early will undergo ET procedures, which include:

- an ETV, and
- posttreatment follow-up visits (Visit 801 and Visit 802).

The investigator will complete any AE reporting and necessary follow-up (Section 8.3).

7.1.1. Liver Chemistry Stopping Criteria

Participants who are discontinued from study drug because of a hepatic event or liver test abnormality should have additional hepatic safety data collected via the hepatic eCRF packet.

Interrupting study drug based on elevated liver tests

The study drug should be **interrupted** and **CC1**

if one or more of these conditions occur:

Elevation	Exception
ALT or AST >8x ULN	
ALT or AST >5x ULN for more than 2 weeks	
ALT or AST >3x ULN and either TBL >2x ULN or INR >1.5	For participants with Gilbert's syndrome: If baseline direct bilirubin is >0.5 mg/dL, then doubling of direct bilirubin should be used for drug interruption decisions rather than TBL>2x ULN.
ALT or AST >3x ULN with the appearance of fatigue, nausea, vomiting, right upper quadrant pain or tenderness, fever, rash, and/or eosinophilia (>5%)	
ALP >3x ULN, when the source of increased ALP is the liver	
ALP >2.5x ULN and TBL > 2x ULN	For participants with Gilbert's syndrome: If baseline direct bilirubin is >0.5 mg/dL, then doubling of direct bilirubin should be used for drug interruption decisions rather than TBL>2x ULN.
ALP >2.5x ULN with the appearance of fatigue, nausea, vomiting, right upper quadrant pain or tenderness, fever, rash, and/or eosinophilia (>5%)	

Source: FDA Guidance for Industry: Drug-Induced Liver Injury: Premarketing Clinical Evaluation, July 2009 and other consensus guidelines, with minor modifications

Resuming study drug after elevated liver tests

Resumption of the study drug can be considered only in consultation with the Lilly-designated medical monitor and only if the liver test results return to baseline and if a self-limited non-drug etiology is identified. Otherwise, the study drug should be discontinued.

7.1.2. Permanent Discontinuation

Possible reasons leading to permanent discontinuation of study drug include, but are not limited to:

Subject Decision

- The participant requests to discontinue the study drug.

Disease Worsening

- The participant requires treatment with a specified prohibited CD medication (Section 10.7, Appendix 7).
- The participant undergoes surgery for CD (with the exception of drainage of a perianal or other cutaneous abscess or seton placement).

Safety Considerations

- The participant has a diagnosis of any of the following during the study:
 - cancer other than squamous cell or basal cell carcinoma of the skin
 - any colonic adenomatous polyp with low grade dysplasia, not completely removed,
 - any adenomatous polyp with high grade dysplasia
 - evidence of dysplasia in non-polypoid mucosa (indefinite for dysplasia, low grade, or high-grade dysplasia) in the GI tract
 - active TB (Section 8.2.6)
 - HIV/acquired immunodeficiency syndrome (AIDS)
 - hepatitis B or development of detectable hepatitis B virus (HBV) DNA under specified circumstances (Section 8.2.8), or
 - hepatitis C or development of detectable hepatitis C virus (HCV) RNA (Section 8.2.9).
- If the investigator determines that a systemic hypersensitivity reaction has occurred related to study intervention administration, the participant may be permanently discontinued from the study intervention, and the sponsor's designated medical monitor should be notified. If the investigator is uncertain about whether a systemic hypersensitivity reaction has occurred and whether discontinuation of study intervention is warranted, the investigator may consult the sponsor.
- The participant has absolute lymphocyte count $<0.5 \times 10^3/\mu\text{L}$ after retesting (see Section 7.1.3).
- The participant has liver chemistry levels outside acceptable ranges that fail to meet the criteria for resumption of study drug as described in Section 7.1.1.
- The participant becomes pregnant. Pregnant participants will not undergo an endoscopy at the ETV (Section 8.1.1.2).

- Noncompliance with LTBI treatment (see Section 8.2.6).
- The participant has an AE or SAE which, in the opinion of the investigator or sponsor, would preclude the participant from continuing to receive study drug.
- It is recommended that the participant be assessed by an appropriately trained professional to assist in deciding whether the participant is to be discontinued if:
 - CCI [REDACTED]
 - the participant reports suicidal ideation or suicidal behaviors during the study.

Other Reasons

- Treatment noncompliance: CCI [REDACTED] (Section 6.4).
- Study participants and physicians may discontinue the study participation if they perceive no clinical benefit.

Participants discontinuing from the study drug prematurely for any reason will complete AE and other follow-up procedures as specified in the SoA (Section 1.3), Section 8.2 (Safety Assessments), and Section 8.3 (Adverse Events and Serious Adverse Events), including ETV and posttreatment follow-up visits (Visit 801 and Visit 802).

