During and after study drug administration, participants should be closely monitored for signs or symptoms of AEs, including hypersensitivity events, other infusion-related events, and infusion or injection site reactions. See Section 8.3.7.2 for more information about blood sampling and data collection.

Hypersensitivity Events

If a participant experiences a systemic hypersensitivity reaction involving 2 or more organ systems (that is, mucocutaneous, respiratory, cardiovascular, or gastrointestinal systems) during or up to 6 hours after an infusion of study drug, the following guidance should be followed:

- Study drug infusion should be stopped immediately, and appropriate supportive care provided according to local standard practice (for example, administration of epinephrine, antihistamine, systemic steroids, and/or bronchodilators).
- After the participant's stabilization, blood samples should be obtained as described in the SoA (Section 1.3).

Note: Results from PK, immunogenicity, **CCI** are not intended for participant management and will not be provided to investigative sites. The participant should be monitored until resolution or stabilization of the symptoms, as clinically appropriate.

- Study drug should be discontinued (Section 7.1.2). The participant should undergo an ETV and posttreatment follow-up procedures after study drug discontinuation.

For severe/generalized nonsystemic hypersensitivity reactions involving a single organ system (e.g., diffuse rash), all of the above should be followed, except the participant may be allowed to continue in the study. Continuation of a participant in the clinical study based on the investigator's assessment of the event must be discussed and agreed upon with the medical monitor. If it is agreed the participant can continue, premedication prior to subsequent study drug administration may be considered, if judged by the investigator to be appropriate for the individual participant.

Other Infusion-Related Events

If a participant experiences a reaction consisting of headache, rigors, and/or temperature $>38^{\circ}\text{C}$ (in the absence of signs or symptoms of a systemic hypersensitivity reaction) during or up to 6 hours after an infusion of study drug, the following guidance should be followed:

- The study drug infusion should be interrupted, and appropriate medical care should be administered (for example, non-steroidal anti-inflammatory drugs, antipyretics, or antihistamines).

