- Blood samples should be obtained as described in Section 8.3.7.2 or the SoA (Section 1.3).
- Resumption of study drug infusion after interruption, possibly at a slower rate of administration, can be considered if symptoms resolve and it is deemed to be medically appropriate based on the investigator's discretion and considering the risk/benefit of readministration.
- Premedication prior to subsequent study drug administration may be considered if judged by the investigator to be appropriate for the individual participant.
- If the participant develops systemic hypersensitivity symptoms or signs, he or she should be managed as described above for a systemic hypersensitivity reaction. The participant should remain in observation, as is clinically appropriate for the participant's symptoms.

Injection Site Reactions or Infusion Site Reactions

If a participant experiences an injection site reaction or an infusion site reaction, such as pain, erythema, urticaria, pruritus, or edema localized to the SC injection or infusion site (in the absence of systemic hypersensitivity signs or symptoms), the following guidance should be followed:

- The participant should be instructed to contact the study site to report any symptoms experienced following a SC injection or an infusion site reaction.
- If the participant develops systemic hypersensitivity symptoms, he or she should be managed as described above for a systemic hypersensitivity reaction.

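### Section 6.7's direction to stop drug after a multi-organ hypersensitivity reaction names infusions; after an SC injection without a site reaction, the visible text leaves stopping to judgement

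*Protocol*

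**What the plan says.** Protocol Section 6.7, under Hypersensitivity Events, defines a systemic reaction as one involving at least two organ systems and occurring "during or up to 6 hours after an infusion of study drug". The first action is "Study drug infusion should be stopped immediately". The last is "Study drug should be discontinued (Section 7.1.2). The participant should undergo an ETV and posttreatment follow-up procedures after study drug discontinuation".

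The same section treats a lesser reaction separately: "For severe/generalized nonsystemic hypersensitivity reactions involving a single organ system (e.g., diffuse rash), all of the above should be followed", except that the participant may stay in the study. Continuation then "must be discussed and agreed upon with the medical monitor".

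Injections enter through the site-reaction paragraph of Section 6.7. It starts from a reaction "localized to the SC injection or infusion site (in the absence of systemic hypersensitivity signs or symptoms", and adds: "If the participant develops systemic hypersensitivity symptoms, he or she should be managed as described above for a systemic hypersensitivity reaction".

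Section 7.1.2 covers any related systemic hypersensitivity reaction, whatever the route or timing. It says that "the participant may be permanently discontinued from the study intervention" and that the medical monitor should be notified; an investigator who is unsure may consult the sponsor.

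**The concern.** The direction to stop is tied to the route that fewer doses use. SC injection is the long-term route. Under Section 6.1, participants or caregivers who choose to do so give the injections themselves after Visit 4, and Continued Access (Section 10.13.3) is built on self-injection. A participant who has a multi-organ reaction to an SC dose, with nothing at the injection site, meets no direction to stop in the visible text. The same reaction during an infusion does.

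The two sections also disagree on the verb. Section 6.7 says *should* and cites Section 7.1.2 for the action; Section 7.1.2 says *may*. At stake is whether someone is re-dosed after a multi-organ reaction.

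**Working it through.** The plan states no figure on this point, so the check sets the provisions side by side.

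| Reaction | Section 6.7 | Section 7.1.2 hypersensitivity bullet |
|---|---|---|
| Multi-organ, within 6 hours of an infusion | Drug should be discontinued; early termination visit and follow-up | May be discontinued; monitor notified |
| Multi-organ after an SC dose, developing from a localized site reaction | Same, through the site-reaction paragraph | May be discontinued; monitor notified |
| Multi-organ after an SC dose, no site reaction | No direction in the visible text | May be discontinued; monitor notified |
| Severe or generalized, single organ, nonsystemic | Same steps, but continuation possible if the monitor agrees; no route named | Not addressed |

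1. **Third row.** The infusion trigger does not name injections, and the site-reaction paragraph presupposes a localized reaction without systemic signs. A reaction that is systemic from the outset, with no site reaction, satisfies neither.

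2. **First row.** Reading Section 6.7 as the stricter, specific rule settles the matter for infusions. But the section it cites permits continuation that Section 6.7 directs against.

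3. **Fourth row.** If the single-organ sentence covers every route, continuing after a diffuse rash from an SC dose needs the monitor's agreement, while the hypersensitivity bullet asks only that the monitor be notified of a multi-organ reaction. If the sentence inherits the infusion limit from the text it refers back to, neither reaction has a direct rule after an SC dose.

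4. **Other provisions that apply to the third row.** These are the AE/SAE reason in Section 7.1.2 (investigator or sponsor opinion), the call in Section 8 for immediate sponsor discussion of safety concerns, the monitor's control over restarting withheld drug in Section 7.1.3, and, in Continued Access, the related-safety-concern reason in Section 10.13.8. Each rests on case-by-case judgement. None sets a stop for this reaction.

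5. **Signs of intent.** The title and opening of Section 6.7 include injections, and Section 6.7.1 names both routes. The sampling footnotes in the Schedule of Activities for systemic hypersensitivity events are not limited by route. The narrow trigger is out of step with the text around it.

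6. **How much dosing lies outside the direct trigger.** The regimen is partly redacted, so assume a dose every 4 weeks from Week 0. Doses to Week 152: 152/4 + 1 = 39. Doses to Week 156: 156/4 + 1 = 40. SAP Section 5.7.3 gives 3 IV doses for re-induced participants, so the direct trigger covers 3/39 = 7.7% or 3/40 = 7.5% of their doses. If such a participant stops after a Week 52 dose, it covers 3/(52/4 + 1) = 3/14 = 21.4%. For participants assigned to SC from the start (SAP Section 2) it covers none. These are shares of doses, not of risk.

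**The case against.** The strongest reply is that this reading is too literal. Section 6.7 opens with monitoring after any administration, asks participants to report symptoms after an SC injection, and sends systemic symptoms to the same pathway. Nobody would sensibly stop drug for a participant with a trivial site reaction plus systemic symptoms and not for one with systemic symptoms alone. That is a fair account of the likely intent, and it lowers confidence. It does not change what the condition in the site-reaction paragraph says.

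Second, *may* in Section 7.1.2 has a reason. Its list is of possible reasons, and its hypersensitivity bullet covers a wider class than Section 6.7: any related systemic reaction, at any time, by any route. A permissive verb suits that wider class. It does not suit the multi-organ reaction for which Section 6.7 directs a stop.

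Third, Section 8.3.7.2, on hypersensitivity, is redacted. Section 6.7 describes it as covering blood sampling and data collection, so a stopping rule there is unlikely, but it cannot be excluded. Section 2.3 also points to guidance in the Investigator's Brochure, which is not available here.

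Four stronger readings are tempting and not supported:

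- A reader might infer that Section 7.1.2's *may* is the sole provision left. The AE/SAE reason and the sponsor discussion in Section 8 also apply.
- A reader might infer that the protocol contemplates unreviewed re-dosing at home. Section 8 asks for immediate discussion of whether to continue or stop, and on entry to Continued Access criterion 38 brings back the Section 5.2 exclusion for known hypersensitivity to mirikizumab.
- A reader might take the dose shares as shares of risk. The two anaphylaxis-consistent events in Section 2.3 were infusion-related, and the documents report no multi-organ reaction to an SC dose.
- A reader might carry the 6-hour window over to injections. No document supports that window for SC dosing.

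**Conclusion.** The point holds for the visible text. A multi-organ reaction after an SC dose without a site reaction is left to discretionary provisions, and Section 7.1.2 does not match Section 6.7 for the reaction that Section 6.7 defines. This is a stated rule with too narrow a scope and a mismatched verb, and it bears on participant safety.

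The expected number of events is small. Section 2.3 reports two anaphylaxis-consistent events with the Phase 2 lyophilized IV product, none after the infusion was lengthened, and no anaphylactic reactions with the Phase 3 formulation. No number exposed is given there, so no rate can be computed.

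Confidence is moderate. The conclusion assumes that the redacted Section 8.3.7.2 holds no stopping rule and that sites follow the wording rather than its probable intent. No effect on the efficacy endpoints is claimed.

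**What to change.** Two wording changes for the next amendment:

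1. **Section 6.7.** Extend the systemic-reaction trigger to *an infusion or injection of study drug*. Keep 6 hours for infusions and let the sponsor set the SC window, or write *during or after an injection*. Reword the first action to *stop the infusion, or withhold any remaining injection of the dose*, since Section 6.1 describes an SC dose as two injections.
2. **Section 7.1.2.** State that study drug *should* be permanently discontinued for a reaction meeting the Section 6.7 multi-organ definition, and that continuing after any other related systemic reaction must be agreed with the medical monitor.

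There is no analysis cost. The downside is a small loss of investigator discretion. If Section 8.3.7.2 or the Investigator's Brochure already holds a stop for SC reactions, a cross-reference in Section 6.7 would replace the first trigger change; the verb in Section 7.1.2 would still need aligning.

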7.1.3. Criteria for Temporary Interruption (Withholding) of Study Drug

Cases that may merit temporary withholding of study drug must be discussed with the medical monitor. The medical monitor, in consultation with the investigator, will determine when it is appropriate to recommence study drug.

Some possible reasons for temporarily withholding of study drug include, but are not limited to:

- The participant develops a clinically important intestinal or extraintestinal infection (including LTBI) during the study (see Section 5.2).
- The participant requires major surgery. Administration of study drug may be restarted only after adequate wound healing.
- The participant develops a confirmed absolute neutrophil count $<1 \times 10^9/\text{L}$ ($<1 \times 10^3/\mu\text{L}$ or $<1 \text{ GI/L}$ (2 assessments below this threshold).
- A participant who develops an absolute lymphocyte count $<500 \text{ cells}/\mu\text{L}$ ($<0.5 \times 10^3/\mu\text{L}$ or $<0.50 \text{ GI/L}$) will be retested every 2 weeks for up to 8 weeks unless the lymphocyte count becomes $\geq 0.5 \times 10^3/\mu\text{L}$ or $\geq 0.50 \text{ GI/L}$.
 - Azathioprine, methotrexate, or 6-mercaptopurine must be discontinued, if applicable, after the first retest confirming absolute lymphocyte count $<0.5 \times 10^3/\mu\text{L}$ (second assessment below threshold), and the next dose of study drug held. The participant must be retested in approximately 2 weeks.
 - The third retest (fourth assessment below threshold) should occur prior to the next monthly dosing and if still below $<0.5 \times 10^3/\mu\text{L}$, the next dose of study drug should also be held. The participant must be retested in approximately 2 weeks.

- After the fourth retest (fifth assessment below threshold), the participant may be permanently discontinued. Consult the medical monitor. White blood cell and lymphocyte counts will be followed for these participants until they return to an acceptable level.
- The participant has laboratory abnormalities that may lead the investigator to hold the study drug until resolution of the abnormalities.

7.2. Participant Discontinuation/Withdrawal from the Study

Participants will be discontinued (withdrawn) from the study in the following circumstances:

- enrollment in any other clinical study involving an investigational product or enrollment in any other type of medical research judged not to be scientifically or medically compatible with this study
- participation in the study needs to be stopped for medical, safety, regulatory, or other reasons consistent with applicable laws, regulations, and good clinical practice (GCP)
- the investigator decides that the participant should be discontinued from the study
- all participants from originator Study AMAM CCI
[REDACTED] and enter the 12- to 16-week posttreatment follow-up period, or
- the participant requests to be withdrawn from the study.

Participants discontinuing from the study prematurely for any reason should have AE and other safety follow-up specified for the ETV. See Section 1.3 (Schedule of Activities), Section 8.2 (Safety Assessments), and Section 8.3 (Adverse Events and Serious Adverse Events).

7.3. Lost to Follow up

A participant will be considered lost to follow-up if he or she repeatedly fails to return for scheduled visits and is unable to be contacted by the study site. Site personnel are expected to make diligent attempts to contact participants who fail to return for a scheduled visit or were otherwise unable to be followed up by the site.

8. Study Assessments and Procedures

Study procedures and their timing, including tolerance limits for timing, are listed in the SoA (Section 1.3). Adherence to the study design requirements, including those specified in the SoA, is essential and required for study conduct.

The disease activity measurements are used in clinical practice and CD clinical trials.

The safety parameters in this study are routine elements of clinical health assessment and Phase 3 drug development.

Safety concerns should be discussed with the sponsor immediately upon occurrence or awareness to determine whether the participant should continue or discontinue study drug.

All screening criteria evaluations must be completed and reviewed to confirm that potential participants meet all eligibility criteria. Timing to receive results and to retest if needed should be considered when scheduling. If the available screening laboratory results are from samples taken more than CCI prior to Visit 1 dosing, new labs should be collected again prior to dosing. The investigator will maintain a screening log to record details of all participants screened and to confirm eligibility or record reasons for screening failure, as applicable.

Unless otherwise stated in the subsections below, all samples collected for specified laboratory tests will be destroyed within 60 days of receipt of confirmed test results. Certain samples may be retained for a longer period, if necessary, to comply with applicable laws, regulations, or laboratory certification standards.

